## 12. ADVERSE EVENTS

### 12.1. Definition of Adverse Events

#### 12.1.1. Adverse Event

An AE is any untoward medical occurrence in a clinical study subject. No causal relationship with the study drug/IMP or with the clinical study itself is implied. An AE may be an unfavorable and unintended sign, symptom, syndrome, or illness that develops or worsens during the clinical study. Clinically relevant abnormal results of diagnostic procedures including abnormal laboratory findings (eg, requiring unscheduled diagnostic procedures or treatment measures, or resulting in withdrawal from the study) are considered to be AEs. Abnormal results of diagnostic procedures that are incidental or not clinically relevant are not reportable as AEs. If the diagnostic procedure prompts no additional treatment, visits, or monitoring, it will not meet the definition of an AE.

This includes the following:

- AEs not previously observed in the subject that emerge during the protocol-specified AE reporting period (see Section 12.4.1).
- Findings from protocol-mandated interventions. This can include laboratory assessments performed in the course of the clinical study. AEs should be reported only if the abnormalities are changes from baseline and are clinically significant as described above.
- Pre-existing medical conditions (other than the condition being studied) judged by the investigator to have worsened in severity or frequency or changed in character during

the protocol-specified AE reporting period. When recording such events on an AE/SAE eCRF page, it is important to convey the concept that the pre-existing condition has changed by including applicable descriptors (eg, “more frequent headaches”).

An adverse reaction is defined in International Council for Harmonisation (ICH) E6 guideline as follows: all untoward and unintended responses to a study drug/IMP related to any dose administered. The definition covers also medication errors and uses outside what is foreseen in the protocol, including misuse and abuse of the product. The definition implies a reasonable possibility of a causal relationship between the event and the study drug/IMP. This means that there are facts (evidence) or arguments to suggest a causal relationship.

Hospitalization scenarios do not require reporting as an SAE where there is no occurrence of an AE. These scenarios include a planned hospitalization or prolonged hospitalization to:

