### 12.4. Method, Frequency, and Time Period for Detecting Adverse Events and Reporting Serious Adverse Events

Reports of all AEs and SAEs, regardless of investigator attribution, are to be collected from the time of enrollment through to the last study visit (ie, through the post-treatment follow-up

visit). If AEs/SAEs occur after the subject has signed the informed consent form (ICF) for Study 205 but while the subject is still enrolled in the prior study, the AEs/SAEs will be collected according to the procedures specified in the prior study protocol. All AEs and SAEs are to be reported on the AE eCRF.

AEs should be documented on the eCRFs as investigators become aware of them. AEs are to be followed until the event resolves. If an event is ongoing at the last follow-up visit, Grade 1 and Grade 2 events do not need to be followed if the event is deemed unlikely to be related or not related to study drug/IMP (see Section 12.2 for AE grading). For all Grade 3 and Grade 4 events or events deemed possibly, probably, or definitely related to use of study drug/IMP, the event should be followed until the AE is resolved or the subject is in a clinically stable condition with regard to the AE.

The investigator shall report all SAEs immediately and no later than 24 hours of their knowledge of the event to the sponsor by communicating with the medical monitor (phone or email) and by entering the event into the AE eCRF and by completion of the SAE eCRF. The SAE eCRF is an additional form to the AE eCRF that provides important details on the SAE. The investigator should follow all unresolved SAEs observed during the study until they are resolved, or are judged medically stable, or are otherwise medically explained.

The investigator should attempt, if possible, to establish a diagnosis based on the presenting signs and symptoms. In such cases, the diagnosis should be documented as the AE and not the individual sign/symptom. If a clear diagnosis cannot be established, each sign and symptom must be recorded individually. Once a diagnosis is made during evaluation or treatment, the investigator will update the AE record with this diagnosis and delete the previously reported signs and symptoms. The rapid reporting of SAEs ensures that the sponsor shall have the necessary information to continuously assess the benefit-risk profile of the study drug in clinical studies.

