## 5. GENERAL CONSIDERATIONS FOR DATA ANALYSES AND HANDLING

This section addresses the definitions, algorithms, imputations, and conventions that will apply to the analysis and handling of the data in general. Complex derivations will be addressed in the detailed discussions of individual summary tables.

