### **5.6.4. Treatment-emergent Adverse Events**

An AE is considered treatment-emergent if its start date is on or after the date of first dose of study treatment in Study 205 or if the AE is on-going from the prior study. If the AE start date is missing and the AE stop date is after the start date of the first dose of study treatment (or the AE is ongoing) then the AE will be considered treatment emergent. If either or both times are missing, then dates alone will be compared. See Section 5.7.2 for incomplete dates or times.

AEs occurring 30 days after the last dose will be considered as TEAEs. All AEs that occurred more than 30 days after the last dose of study treatment will be excluded from the tables and listings. AEs that occurred during the dose tapering period will be included in the tables and listings. Adverse events that rolled over from the parent study are excluded from the tables but will be included in the listings.

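### SAP 5.6.4 counts every AE ongoing from the prior study as a TEAE but bars all rolled-over AEs from the tables, so whether a worsening in Study 205 is tabulated depends on how the site records it

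*SAP*

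**What the plan says.** SAP 5.6.4 gives two main routes to treatment-emergent status: onset on or after the first Study 205 dose, "or if the AE is on-going from the prior study". The second route does not require the event to have changed. The section counts AEs up to 30 days after the last dose and ends with the display rule: "Adverse events that rolled over from the parent study are excluded from the tables but will be included in the listings".

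SAP 8.1 and 8.2 define the AE tables on TEAEs and add no rule for carried-over events. The SAP 8.1 event percentages use the total number of TEAEs as denominator. The overall, SOC/PT, serious and non-serious tables are split into 400 mg BID, dose taper and Total.

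On recording, Protocol 12.1.1 treats as an AE a pre-existing condition, other than the disease under study, that is "judged by the investigator to have worsened in severity or frequency or changed in character" in the reporting period. For the eCRF page it says "it is important to convey the concept that the pre-existing condition has changed by including applicable descriptors". Protocol 12.4 adds "AEs are to be followed until the event resolves", and for serious events "The SAE eCRF is an additional form to the AE eCRF that provides important details on the SAE".

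**The concern.** Subject incidence of graded TEAEs is part of the study endpoint (Protocol 6.2, SAP 2.2). Protocol 13.3.4 asks for the proportions of subjects with TEAEs, with treatment-emergent SAEs and with Grade 3 or 4 TEAEs, and does not set carried-over events aside. SAP 9 does not name the exclusion as a change from the protocol.

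Every subject enters after at least 12 weeks on BCX9930. Exclusion criterion 2 bars ongoing AEs judged to compromise participation or benefit-risk, but other AEs can be open at rollover. If one of these later reaches Grade 3 or 4 or becomes serious, a reader of the tables would expect to find it there. Under 5.6.4 its presence depends on site recording practice, which neither document settles. A second, smaller problem is that tables and listings with the same TEAE title do not contain the same events.

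**Working it through.** The plan gives no figure to reproduce: there is no sample size calculation and no hypothesis test. The check is mainly textual.

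**Step 1: label against content.** By definition, TEAEs are new-onset AEs plus all AEs ongoing from the prior study. The tables hold that set minus all rolled-over AEs; the listings keep them.

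| Subject | Table | Listing |
|---|---|---|
| All TEAEs | 14.3.2.1 | 16.2.7.1 |
| Renal TEAEs | 14.3.2.4 | 16.2.7.3 |
| Hepatic TEAEs | 14.3.2.5 | 16.2.7.4 |

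Three pairs therefore share a label but not an event set. All six AE tables in SAP 9.1.1 fall under the exclusion: 14.3.1.1, 14.3.2.1, 14.3.2.3.1, 14.3.2.3.2, 14.3.2.4 and 14.3.2.5.

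**Step 2: follow one event.** Suppose an AE is Grade 1 at rollover and becomes Grade 3 and serious in Study 205.

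- The site enters a new AE with a Study 205 start date. It meets the onset criterion and is tabulated.
- The site updates the existing record. The event is still one that rolled over. It is absent from the overall table, including the Grade 3/4 and serious rows, from the SOC/PT and serious tables, and from the renal or hepatic table if it belongs there.

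**Step 3: does the protocol fix the route?** Protocol 12.1.1 asks for a description of the change on the eCRF page, which points to a separate entry. It does not say that an AE already open at rollover must be re-entered. Protocol 12.4 has AEs followed to resolution and has each SAE entered into the AE eCRF with an extra SAE form. It does not say whether an AE already on file that turns serious gets a new AE line. Both routes remain open.

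**Step 4: scale.** For a subject with no other event in the row, the change in subject incidence is 100 × 1/N percentage points.

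- N = 30 (planned maximum): 100/30 = 3.3
- N = 20 (assumed): 100/20 = 5.0
- N = 10 (assumed): 100/10 = 10.0

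A subject already counted in the row does not change subject incidence. The documents do not give the number of carried-over or worsened AEs, so no total effect can be computed.

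**Step 5: event denominator.** The definition would put rolled-over AEs into the SAP 8.1 total; the display rule would leave them out. As an illustration, assume 60 new TEAEs with 6 in a category. Without rolled-over AEs the share is 6/60 = 10.0%. With 10 of them it is 6/70 = 8.6%, and with 20 it is 6/80 = 7.5%. The display rule is the more natural reading for a table, but SAP 8.1 should say so.

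**Step 6: identifying rolled-over events.** SAP 5.7.2 applies the medication date rules of 5.7.1 to AEs. A partial start date in the month or year of dosing can be set to the first-dose date, so a carried-over AE can look new. Rolled-over status cannot safely be read from an imputed date.

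**The case against.** The strongest reply is that the protocol leans towards a new entry. Protocol 12.1.1 places worsening inside the Study 205 reporting period and gives an example term worded as a changed event. Protocol 12.4 has SAEs entered into the AE eCRF. Sites that follow this lead produce a tabulated event. This stands, and it makes the omission conditional. It does not close the gap, because nothing requires a new record for an AE already open.

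The second reply is that the outputs already help. The listings keep these events, Listing 16.2.7.2 covers SAEs, and Listing 16.2.8 shows Grade 3 or 4 laboratory abnormalities. SAP 5.3 allows explanatory footers and SAP 9.1 allows retitling without a SAP revision, so a footnote could cure the label mismatch. This also stands for the labels. A footnote does not put a worsened event into a table.

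A reader might infer three stronger points that the documents do not support.

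- *The table content is undefined.* SAP 5 presents its rules as "conventions that will apply to the analysis and handling of the data in general", so the last sentence of 5.6.4 works as a display rule, and a programmer has one instruction for which events to tabulate.
- *The protocol directs worsening into the existing record.* The sentence "Once a diagnosis is made during evaluation or treatment, the investigator will update the AE record with this diagnosis" might be read that way. It concerns replacing symptoms by a diagnosis, which is relabelling, and does not show that a worsening is missed.
- *No date of worsening is needed.* The EOS/ET visit is planned 21 ± 3 days after the last dose (days 18 to 24), inside the 30-day limit. That timing is only planned and approximate, and four of the tables separate 400 mg BID from dose taper, so a date is needed to place the event.

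**Conclusion.** The concern holds and should be fixed. SAP 5.6.4 uses one label for two event sets, and its exclusion can keep a Grade 3 or 4 or serious worsening out of the endpoint tables when the site updates an existing record. The textual finding is firm; the practical effect depends on eCRF practice that the documents do not describe.

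The size is modest: 3.3 percentage points per affected subject in a row at N = 30, more if fewer enrol, and nothing for a subject already counted there. It would be wrong to read this as lost safety data or as a known understatement of the TEAE rate, because the events remain in the listings and the number affected is unknown. The study is descriptive, with no hypothesis test that could be affected.

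**What to change.** Revise SAP 5.6.4 as follows.

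1. Define a TEAE as an AE with onset on or after the first Study 205 dose, or an AE ongoing from the prior study that, on or after that dose, rises in severity or frequency, alters in character (the Protocol 12.1.1 terms) or becomes serious. Keep the existing 30-day limit. Tabulate all of these.
2. List unchanged carried-over AEs with a 'carried over' flag and do not call them TEAEs.
3. State in 8.1 and 8.2 that counts and the event denominator follow this rule.
4. Take rolled-over status from the prior-study AE record, not from an imputed start date.
5. Count an event once if it has both an updated and a new record.
6. Where worsening is held only in the existing record, identify it in data review before lock. Record the date of worsening or of becoming serious, so that the event can be assigned to the 400 mg BID or dose taper column and checked against the 30-day limit. If the date cannot be established, count the event in the Total column with a footnote.

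The text change is small: the ongoing-AE clause and last sentence of 5.6.4, a line in 8.1/8.2 and a listing flag. SAP 1 allows revision before database lock. The real cost is matching records against Studies 201, 202 and 203, plus one data review, for up to 30 subjects. This assumes that grade and seriousness at rollover can be recovered from the prior-study records. Protocol 5.2.1 says the studies are closely aligned but does not confirm that point.

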### **5.6.5. Concomitant Medications**

A medication will be classified as prior if it stopped before the first dose of study treatment; that is, its end date is on or before the date of the first dose of study treatment. A medication will be classified as concomitant; if the start date is on or after the date of the first dose of study treatment in Study 205, or its end date is after the start date of the first dose of study treatment in Study 205, or the medication is flagged as ongoing. See Section 5.7.1 for incomplete dates.

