#### **Duration of Treatment:**

Each subject will be eligible to receive study drug (BCX9930) under this protocol for up to 96 weeks as long as the investigator believes it is in the subject's best interest to continue treatment, or until the subject has access to other therapy for PNH, whichever comes first. Treatment with BCX9930 will be discontinued for subjects who are deriving no meaningful clinical benefit, or who experience an unacceptable drug-related AE or are otherwise intolerant of study drug.

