**Table 2: Study BCX9930-205: Schedule of Study Assessments/Procedures**

Assessment/Procedure	Baseline Day 1 a	Treatment Period (Weeks 8, 16, 24, 32, 40, 48, 60, 72, 84, and 96 b )	EOS/ET c
Written informed consent	X		
Review eligibility criteria	X		
Medical & medication history d	X		
HBV, HCV, HIV viral load testing e			
Height, body weight & BMI	X		
Symptom-directed physical examination f	X	X	X
Vital signs g	X	X	X
Clinical chemistry h /hematology i /coagulation/ urinalysis including microscopy j	X	X	X
Pregnancy test k	X	X	X
FSH test l	X	X	X
Study drug administration m			
Study drug accountability	X	X	X
Record AEs, concomitant medications & transfusions	X	X	X

Abbreviations: AE = adverse event; BID = twice daily; BMI = body mass index; EOS = end of study; ET = early termination; FSH = follicle-stimulating hormone; HBV = hepatitis B virus; HBC = hepatitis C virus; HIV = human immunodeficiency virus; ICF = informed consent form; PNH = paroxysmal nocturnal hemoglobinuria; RBC = red blood cell; WBC = white blood cell.

a The last on-treatment visit completed for the prior study will also serve as the baseline visit for Study 205. Therefore, procedures at the last on-treatment visit in the prior study and any specific assessments for Study 205 will be conducted at this visit. If there will be a lapse between the end of the prior study and rollover into Study 205 such that the baseline visit for Study 205 is not conducted coincident with the last on-treatment visit in the prior study, the site must contact the sponsor medical monitor (or designee) to determine whether the subject will be eligible to participate in Study 205. If eligible and subsequently enrolled into Study 205, the subjects must complete the Study 205 baseline visit. The sponsor medical monitor (or designee) will recommend which procedures need to be performed at that visit.

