### **12.5.3. Risk of Hemolysis After Missed Doses, Treatment Interruption, or Permanent Discontinuation**

Investigators should remind subjects of the potential risk of hemolysis following missed doses (particularly multiple consecutive missed doses) and treatment interruption, and the definite risk after permanent discontinuation of BCX9930. By inhibiting the AP of complement, BCX9930 may improve Hb levels and increase circulating RBC clone size by reducing the hemolysis of PNH RBCs. Missed doses and treatment interruption of BCX9930 may lead to hemolysis. Subjects are at risk of severe hemolysis when BCX9930 is permanently discontinued. Based on available data regarding the PK and PD of BCX9930, severe hemolysis, if it occurs, would be expected to present within days after discontinuation of therapy.

Monitoring for hemolysis should be performed based on the medical judgement of the investigator. However, when subjects permanently discontinue BCX9930 at any time during the study, the following recommendations are made:

- If the subject is asymptomatic, it is recommended that contact with the subject be maintained on a daily basis for a minimum of 7 days. Contact may be conducted by telephone, email, or other means, including in person, if preferred. When any sign or symptom of hemolysis occurs, the subject should be promptly evaluated. Additional monitoring following the first contact after permanent discontinuation should be guided by the medical judgement of the investigator.

- For subjects who are already symptomatic when treatment is discontinued, whether the subject should be assessed in person or can be followed with daily contact will be based on the investigator's medical judgement taking into account the severity of the reported signs or symptoms and/or any reported worsening of the signs or symptoms. When possible, subjects should return to the investigative center; however, when this is not possible, arrangements may be made for the subject to be assessed by his or her local hematologist and a local laboratory used for clinical laboratory testing. When hemolysis occurs after the permanent discontinuation of BCX9930, treatment should be provided according to the judgement of the investigator.

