### **5.6.8. Number of Units of Packed RBCs Transfused**

The number of units of pRBCs will be the total count per subject of units of pRBCs or whole blood that are administered to the subject during the study as recorded in the eCRF. Transfusions of 1 unit of whole blood will count as 1 unit of pRBCs.

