### **5.7.1. Missing Start and Stop Dates for Concomitant Medication**

For analysis of medications, a complete date should be established to identify medication as occurring during treatment or not. For the purposes of handling partially reported start and stop dates for medication, the following algorithm will be applied:

- Missing start day, but month and year present:  
If study medication had been taken in the same month and year as the occurrence of the medication, then the start day of the medication will be assigned to the day of first dose of study medication.  
Otherwise, the start day will be set to the first day of the month.
- Missing start day and month, but year present:  
If study medication had been taken in the same year as the occurrence of the medication, then the start date of the medication will be assigned to the date of first application of study medication.  
Otherwise, the start day and month will be set to 01 January.
- Missing end day, but month and year present:  
The day will be set to the last day of the month.

- Missing end day and month, but year present:  
The end day and month will be set to the end of study date.

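### SAP 5.6.5 sets no last-dose limit, so medication first started after BCX9930 has been stopped is tabulated as concomitant under the BCX9930 group

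*SAP*

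**What the plan says.** **Medication rule.** SAP 5.6.5 defines two classes, prior and concomitant, both relative to the first dose. A medication is concomitant "if the start date is on or after the date of the first dose of study treatment in Study 205", or if it ended after the first dose, "or the medication is flagged as ongoing". The last dose is not mentioned. SAP 6.3.1 puts the result in Table 14.1.5.1 for the BCX9930 treatment group.

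**Purpose.** SAP 5.7.1 says that "a complete date should be established to identify medication as occurring during treatment or not".

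**What is collected after the last dose.** The row "Record AEs, concomitant medications & transfusions" in Protocol Table 2 is marked at EOS/ET as well as at baseline and the treatment visits. Footnote c and Protocol 10.1 place EOS/ET about 3 weeks (± 3 days) after the last dose.

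**Why new therapy may start then.** Under Duration of Treatment in the protocol synopsis, BCX9930 continues for up to 96 weeks while the investigator judges it to be in the subject's interest, "or until the subject has access to other therapy for PNH, whichever comes first". Protocol 7.4.1 lists qualifying for an available alternative as a reason for discontinuation. Protocol 12.5.3 expects severe hemolysis, if it occurs, within days of stopping, and adds: "When hemolysis occurs after the permanent discontinuation of BCX9930, treatment should be provided according to the judgement of the investigator".

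**Adverse events, by contrast.** SAP 5.6.4 does set an end: "All AEs that occurred more than 30 days after the last dose of study treatment will be excluded from the tables and listings".

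**Transfusions.** SAP 5.6.8 totals units "administered to the subject during the study as recorded in the eCRF". The only planned transfusion output is Listing 16.2.4.5.

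**The concern.** A rule with a lower limit and no upper one cannot tell a drug taken alongside BCX9930 from a drug taken because BCX9930 was stopped. In this study the second kind is foreseeable, because moving to another PNH therapy is one of the planned ways out. The study is titled as monotherapy, and Table 14.1.5.1 is the only planned medication table. A reader who sees a second PNH therapy there, under the BCX9930 heading, would reasonably take it as combined use. The SAP's stated reason for dating medications is to prevent that confusion.

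A smaller drafting fault lies in the same section. It describes a prior medication as one that stopped before the first dose, then defines this as an end date on or before that dose. The two classes can therefore overlap.

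**Working it through.** The documents state no expected number of switches, transfusions or affected subjects, so there is no figure of the plan's own to reproduce.

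**1. The window.** 3 weeks = 21 days. 21 − 3 = 18 and 21 + 3 = 24, so medications are recorded for 18 to 24 days after the last dose in subjects who attend EOS/ET on schedule.

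**2. The rule applied literally.** Let the first dose be Day 1 and the last dose Day L. Take a medication started on Day L + 5 and still ongoing (an illustrative date).

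- SAP 5.6.5: L + 5 ≥ 1 is true for any L, so it is concomitant. The ongoing flag gives the same answer.
- With the added condition start ≤ L: L + 5 ≤ L is false, so it is post-treatment.

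The result is the same for L = 56, 168, 336 and 672 (8, 24, 48 and 96 weeks × 7).

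**3. Share of recorded time after the last dose.** Share = f / (L + f), with f the days of follow-up. The stopping weeks are assumptions, chosen to show the range.

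| Stop | L (days) | f = 18 | f = 21 | f = 24 |
|---|---|---|---|---|
| Week 8 | 56 | 18/74 = 24.3% | 21/77 = 27.3% | 24/80 = 30.0% |
| Week 24 | 168 | 18/186 = 9.7% | 21/189 = 11.1% | 24/192 = 12.5% |
| Week 48 | 336 | 18/354 = 5.1% | 21/357 = 5.9% | 24/360 = 6.7% |
| Week 96 | 672 | 18/690 = 2.6% | 21/693 = 3.0% | 24/696 = 3.4% |

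These are shares of time, not of subjects or of medications. They show that the open window matters more for early stoppers.

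**4. Partial dates.** Under SAP 5.7.1, a start date with only the year known is set to the first-dose date if study drug was taken in that year. A date lacking only the day is handled in a similar way when study drug was taken in that month. A replacement therapy begun in the same month or year as the last dose can therefore be dated back to the first dose. A start month or year wholly after dosing goes to the first of the month or 1 January, which is after the last dose. A last-dose limit alone would thus leave the ambiguous dates as concomitant, so the SAP needs to state that convention.

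**5. Same-day overlap.** Take a medication that starts and ends on the first-dose date. Its end date is on or before the first dose, so it is prior. Its start date is on or after the first dose, so it is also concomitant.

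**The case against.** **The open window has a use.** Events up to 30 days after the last dose count as TEAEs (SAP 5.6.4), and EOS/ET falls inside that period. SAP 8.1 also tabulates serious TEAEs requiring concomitant medication. If the class simply ended at the last dose, treatment given for such an event shortly afterwards would no longer be concomitant under 5.6.5, and that row would become unclear. This stands. It is a reason to show post-treatment medication separately and not to remove it. It does not justify mixing the two kinds in one column.

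**The timing can be recovered.** With up to 30 subjects, and listings of disposition, medications and exposure all planned, a careful reader could work out when each drug began. That is true and limits the harm, but the summary table would still carry the wrong label.

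**Few subjects may be affected.** Entry requires no access to other effective options, and a misclassified drug must start after the last dose and be recorded by EOS/ET. This also stands. No count can be given.

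**The same-day overlap changes little.** No prior-medication output is planned, and a drug taken only on that day still appears as concomitant. This is a tidying point.

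**Conclusion.** The point holds for the medication rule. Followed exactly, SAP 5.6.5 places medication first started after the last BCX9930 dose, including replacement PNH therapy, in Table 14.1.5.1 as concomitant, against the aim stated in 5.7.1. The error is confined to labelling in one descriptive table, over 18 to 24 days per subject, and applies to subjects followed to EOS/ET who start a drug in that time. How many there are depends on switching rates and dates that the documents do not give.

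A reader might infer more, and the documents do not support it:

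- **That transfusion totals are biased against BCX9930.** SAP 5.6.8 counts units during the study and does not describe them as received with BCX9930. No planned table reports units. What remains is an undivided total behind a listing.
- **That the Hb and LDH summaries are distorted.** SAP 7.1 and 7.2.1 restrict them to scheduled visits in the treatment period, and Protocol Table 2 keeps EOS/ET in its own column. A drug begun after the last dose comes after the on-treatment values.
- **That the table would show breaches of the prohibited-medication rules.** The excluded medications in Protocol 9.8.1 are redacted, so this cannot be judged.

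**What to change.** **SAP 5.6.5.** Use three classes that do not overlap:

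- *Prior*: end date strictly before the first-dose date.
- *Concomitant*: taken at any time from first through last dose, with taper counted as treatment. A drug begun during taper stays here. A drug that ended on the first-dose date moves here from prior.
- *Post-treatment*: start date after the last dose, whether or not flagged as ongoing.

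**Outputs.** Show post-treatment medication as a separate column or section of Table 14.1.5.1. Flag it in Listing 16.2.4.3, with replacement PNH therapies identified.

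**SAP 8.1.** State that medication given for a TEAE within 30 days after the last dose still counts for the row on serious TEAEs requiring concomitant medication.

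**SAP 5.7.1.** State that a start date whose known parts place it after the last dose is never imputed back to the first dose. On a literal reading the present text already does this, and the sentence makes it explicit. Where timing relative to the last dose is ambiguous, treat the medication as concomitant.

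**Transfusions.** Add an on-treatment/post-treatment flag to Listing 16.2.4.5. No new summary is needed.

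**Cost.** A few lines of SAP text, a small programming change and one extra table column. SAP Section 1 allows revision until the plan is final, which must be before database lock. A departure from the final approved plan would be noted in the CSR.
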